6.1.1. Sensitivity/Robustness Analyses (if needed)

The Disagreement Rate between investigator's assessment and ICR's assessment for OR will be calculated in Cohort 1 in the safety analysis population.

Derived ORR per mRECIST v1.1 based on tumor assessment per ICR will be calculated in Cohort 1 in the safety analysis population(details can be found in [Appendix 1](#)).

Sensitivity analyses may be conducted calculating the same ORRs relative to the PP set, if applicable.

6.2. Secondary Endpoint(s)

6.2.1. OR in Cohort 2

The OR in Cohort 2, will be summarized in a similar way as OR in Cohort 1. The estimate of ORR and the corresponding 95% CI will be provided. The frequency (number and percentage) of patients with BOR of CR, PR, SD, PD, non-CR/non-PD (applicable only to patients with non-measurable disease at baseline), and NE (not-evaluable) will be tabulated. The waterfall plot and spider plot will be presented.

6.2.2. Intracranial Objective Response (IC-OR) in Both Cohorts

The IC-OR, will be summarized similar to OR as described above in the subset of the SA population with at least 1 intracranial lesion.

Intracranial ORR is defined as the percent of patients with intracranial response (ie, Best Overall Intracranial Response as confirmed CR or confirmed PR considering only the Lesions having Disease Site=Brain) relative to patients with Brain lesions at study entry, and will be provided along with the corresponding 95% confidence interval. This includes patients for whom the brain lesions have been chosen as RECIST target lesions or not. Surgery or radiotherapy of extracranial lesions will not affect the determination of IC-OR.

6.2.3. Duration of Response (DoR) in Both Cohorts

DoR is defined as the time from the first documentation of CR or PR to the first documentation of disease progression or death due to any cause, whichever occurs first.

DoR will only be calculated for the subgroup of patients with a confirmed objective tumor response. DoR will be summarized in this subgroup using Kaplan-Meier methods and will be displayed graphically where appropriate. The median event time (if applicable) and 2-sided 95% CI for the median will be calculated according to Brookmeyer and Crowley.² If the number of patients with a confirmed CR or PR is small and the use of Kaplan-Meier methods may be limited, the DoR will be listed.

In case the number of patients with Progressive Disease after a confirmed CR or PR is small, the use of Kaplan-Meier method may be limited so the DR and IC-DR will be summarized using Number (%) of Subjects Censored with DR less than 6 months, $\geq 6 - < 9$, $\geq 9 - < 12$, $\geq 12 - < 15$, $\geq 15 - < 18$, $\geq 18 - < 21$, $\geq 21 - < 24$, ≥ 24 months.

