- Progression-free survival (PFS) as assessed by RECIST v1.1 per ICR assessment and investigator assessment, and Overall survival (OS) in both Cohorts.
- Intracranial Objective Response (IC-OR), Duration of response (DoR), Duration of intracranial response (IC-DoR), Time to tumor response (TTR) as assessed by RECIST v1.1 per ICR assessment and investigator assessment, in both Cohorts.
- Safety: adverse event (AE); laboratory abnormalities; electrocardiography (ECG), left ventricular ejection fraction (LVEF), CNS effects.
- PK parameters on Day 1 of Cycle 1 and at steady state: C_{max} (maximum serum concentration), T_{max} (time to reach the maximum concentration), AUC_t (area under the plasma concentration versus time profile from time 0 to time t), AUC_{tau} (area under the plasma concentration versus time profile within a dose interval) at steady state. AUC_{inf} (area under the plasma concentration versus time curve to infinity), CL/F (oral plasma clearance), and V_z/F (apparent volume of distribution) and $t_{1/2}$ (terminal elimination half-life), R_{ac} (accumulation ratio) as data permit.

CCI

STUDY DESIGN

Study overview

This is a Phase 2, multicenter (at approximately 30 sites), dual-cohort study in China, in which approximately 100 patients with locally advanced or metastasis ALK-positive NSCLC will be enrolled to receive lorlatinib monotherapy. In Cohort 1 approximately 66 patients whose disease has progressed after crizotinib will be enrolled, and in Cohort 2, approximately 34 patients whose disease has progressed after ALK inhibitor other than crizotinib. The study design is illustrated below.

Study Treatments

All the patients enrolled into the study will receive lorlatinib monotherapy at the recommended Phase 2 dose (RP2D) of 100 mg QD (quaque die; every day), administered as 4 x 25 mg oral tablets, continuously.

The study treatment may continue until disease progression confirmed by independent central radiology (ICR) review, global deterioration of health status requiring permanent discontinuation per the investigator's judgement, unacceptable toxicity, pregnancy, significant protocol violation, patient lost to follow-up, or patient refusal, the study is terminated by the sponsor, or the death, whichever comes first.

Statistical Methods

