9.3.2. Analysis of Secondary Endpoints

- OR in Cohort 2: The estimated ORR and corresponding exact 2-sided 95% CI will be provided.
- Intracranial objective response (IC-OR): IC-OR is defined the same as OR, but limited to Intra Cranial lesions only on subjects with CNS metastases (ie, Best Overall Intracranial Response as confirmed CR or confirmed PR considering only the lesions having disease site as Brain). Intracranial ORR is defined as the percent of subjects with IC-OR relative to subjects with brain lesions at study entry in the SA set. The estimated IC-ORR and corresponding exact 2-sided 95% CI will be provided.
- Duration of Response (DoR):

DoR is defined as the time from the first documentation of CR or PR to the first documentation of disease progression or death due to any cause, whichever occurs first.

DoR will only be calculated for the subgroup of subjects with a confirmed objective tumor response. DoR will be summarized in this subgroup using Kaplan-Meier methods and will be displayed graphically where appropriate. The median event time (if applicable) and 2-sided 95% CI for the median will be provided. If the number of subjects with a confirmed CR or PR is small and the use of Kaplan-Meier methods may be limited, the DoR will be listed.

The above analyses will be repeated also for the IC-DoR in the subgroup of subjects with IC-OR.

- Time to Tumor Response (TTR):

TTR is defined as the time from first dose to first documentation of objective tumor response (CR or PR). TTR will only be summarized for the subgroup of subjects with an objective response. Descriptive statistics mean, median and range will be provided.

- Progression-free Survival (PFS):

PFS is defined as the time from first dose to first documentation of objective disease progression or to death due to any cause, whichever comes first.

PFS will be summarized using the Kaplan-Meier method and displayed graphically where appropriate. The median event time (if applicable) and 2-sided 95% CI for the median will be reported.

- Overall Survival (OS)

OS is defined as the time from first dose to the date of death due to any cause.

OS will be summarized using the Kaplan-Meier method and displayed graphically where appropriate. The median OS (if applicable) and 2-sided 95% CI for the median will be reported.

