2. INTRODUCTION

This SAP provides the detailed methodology for summary and statistical analyses of the data collected in study B7461024. This analysis plan is meant to supplement the study protocol. Any deviations from this analysis plan will be described in the Clinical Study Report.

The primary analysis will include all data up to a data cutoff date which will be determined by the data maturity and is currently estimated to be around 8 months after last subject first dose in study B7461024. All summaries and analyses will include all data pertaining to visits/assessments performed up to and including the data cutoff date.

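### SAP 6.2.3 should not let a small number of progressions move DoR and IC-DoR from Kaplan-Meier to a table of censored responders

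*SAP*

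**What the plan says.** DoR and IC-DoR are secondary endpoints in both cohorts. SAP 6.2.3 sets the default: "DoR will be summarized in this subgroup using Kaplan-Meier methods and will be displayed graphically where appropriate". On the median it adds: "The median event time (if applicable) and 2-sided 95% CI for the median will be calculated according to Brookmeyer and Crowley". Two departures follow.

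- **Few responders.** When confirmed responders are few and Kaplan-Meier is of limited use, individual DoR values go into a listing. Protocol 9.3.2 has the same rule, opening with "If the number of subjects with a confirmed CR or PR is small".
- **Few progressions.** The trigger reads: "In case the number of patients with Progressive Disease after a confirmed CR or PR is small, the use of Kaplan-Meier method may be limited". What then happens is given in these words: "so the DR and IC-DR will be summarized using Number (%) of Subjects Censored with DR less than 6 months". Further bands run to 24 months or more. Protocol 9.3.2 has no counterpart to this rule.

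SAP 6.2.4 has IC-DoR summarised in the same way as DoR.

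Two general sections also bear on the point. SAP 5.2.17 has time-to-event endpoints summarised by Kaplan-Meier, with medians, quartiles, probabilities at chosen times, log(-log) intervals for those probabilities, and counts of patients with an event. SAP 5.3 provides the entry NR for a statistic that is not reached. Sections 6.2.6 (PFS) and 6.2.7 (OS) commit to rates at specific times with 95% CIs; section 6.2.3 does not.

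The data cutoff for the primary analysis is "currently estimated to be around 8 months after last subject first dose in study B7461024".

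**The concern.** The second departure rests on a premise that does not hold. Kaplan-Meier does not fail when events are few. The median may not be reached, but the curve, the rates at fixed times and their intervals remain available.

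The substitute has four weaknesses:

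- It bands only censored responders, so it does not show when the other responses ended.
- It names no estimate and no interval.
- 'Small' has no threshold, so the choice of method would be made once the event count is visible.
- The trigger counts progression only, although the SAP's DoR definition also counts death.

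If the table replaces Kaplan-Meier, a secondary endpoint in both cohorts would be reported largely as time from response to last assessment. It would happen when few responses have ended, which is the favourable outcome and the one in which a reader most wants a durability estimate.

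**Working it through.** **Inputs from the documents.** Cohort 1 has N = 66 and a design ORR of 30% + 20 points = 50% (SAP 5.1.1), so 66 × 0.50 = 33 responders. The cutoff is about 8 months after the last first dose (SAP 2). Scans are every 6 weeks (Protocol 7.1), and 1 month = 30.4375 days (SAP 5.2.14). The plan states no event count, power or threshold for DoR, so there is no DoR figure to reproduce. The design figures do reproduce: 28 or more of 66 gives exact one-sided alpha 0.0216 and power 0.912, and 17/34 gives a 95% CI width of 35.1%.

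**Assumptions not in the documents.** First response at 6 weeks; uniform accrual over A = 6, 12 or 18 months; 20 intracranial responders; exponential DoR with a median of 15 to 30 months. In steps 2 and 3, follow-up after response runs to the cutoff, from 8 − 42/30.4375 = 6.6 months to 6.6 + A months, evenly spread.

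**1. Is Kaplan-Meier usable with few events?** Take 33 responders, 5 events by 6 months and no earlier censoring.
- S = 28/33 = 0.848, and −ln S = 0.164.
- The standard error on the log(-log) scale is √[5/(33 × 28)] / 0.164 = 0.448.
- The limits are exp{−exp[ln(0.164) ± 1.96 × 0.448]}, that is 67.4% to 93.4%.

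With 3 events, S = 30/33 = 90.9% (74.4% to 97.0%). The exception is zero events by the landmark: the rate is 100% and no log(-log) interval exists.

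**2. Does the table distinguish durable from less durable responses?** Take 33 responders, A = 12, and 5 events placed in the five responders with the longest follow-up.

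| | Events at 1.4 months (all 5) | Events at 6.9, 7.5, 8.3, 8.3, 8.3 months |
|---|---|---|
| Censored, <6 months | 0 | 0 |
| Censored, 6 to <9 | 7 | 7 |
| Censored, 9 to <12 | 8 | 8 |
| Censored, 12 to <15 | 8 | 8 |
| Censored, 15 to <18 | 5 | 5 |
| Censored, 18 or more | 0 | 0 |
| Kaplan-Meier, 6 months | 84.8% (67.4% to 93.4%) | 100% (no log(-log) CI) |
| Kaplan-Meier, 9 months | 84.8% (67.4% to 93.4%) | 82.7% (63.3% to 92.5%) |

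The tables are identical, but the 6-month rates differ by 15.2 points.

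**3. Does the table move when durability does not?** Hold 3 events at 1.4, 2.8 and 4.1 months, so that 6-month DoR stays at 90.9%.
- A = 6: the 30 censored responders fall 12/15/3 in the bands 6 to <9, 9 to <12 and 12 to <15.
- A = 18: they fall 4/5/5/5/5/4/2 across the bands from 6 to <9 up to 24 or more.

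Only accrual time changed.

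**4. How many events might there be?** For A = 12, average 1 − exp(−ln 2 × u/m) over u from 6.6 to 18.6 months.
- m = 30 gives 0.250, so 33 × 0.250 = 8.3 events.
- m = 15 gives 0.434, so 33 × 0.434 = 14.3 events.
- With 20 intracranial responders, the counts are 5.0 and 8.7.

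The 5-event illustrations therefore lie below the Cohort 1 range and at the lower end of the intracranial one.

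**5. What can the cutoff support?** SAP 5.2.9 has assessment dates used for censoring. Eight months is 8 × 30.4375/7 = 34.8 weeks, so the last patient's latest nominal scan is at week 30. With response at week 6, DoR is censored at 24 weeks: 168/30.4375 = 5.5 months. The latest-enrolled responders can therefore be censored before 6 months, and the no-earlier-censoring condition in step 1 is an idealisation. With A = 6, the longest follow-up to cutoff is 6.6 + 6 = 12.6 months, so almost nobody would be at risk at 12 months.

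**The case against.** The strongest reply is that the SAP never says Kaplan-Meier is dropped. Section 6.2.3 first commits to it without condition, then says only that it may be limited. Section 5.2.17 calls for Kaplan-Meier estimates and event counts for time-to-event endpoints in general. Read together, the banded table could be an addition. This reading is open, and a reader who infers that the SAP definitely abandons Kaplan-Meier goes beyond the text. Replacement remains the more natural reading, because the specific section gives the limitation as its reason for the other summary and does not say that the general outputs are kept.

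Three further inferences are tempting and not supported:

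- **That responders whose responses ended disappear.** Their total follows by subtracting the censored count from the number of responders, and section 5.2.17 asks for event counts. What the table loses is when those responses ended.
- **That departing from the protocol is itself an error.** Protocol 9 lets the SAP modify its outline and reserves amendments for major changes to the primary endpoint or its analysis.
- **That the trigger will probably be met.** Step 4 rests on assumed accrual, DoR medians and intracranial responder numbers. Nothing in the documents says whether 8 of 33 would count as small.

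It is also fair that DoR is descriptive and carries no test, and that PFS keeps its full Kaplan-Meier analysis. PFS does not answer the question of durability among responders.

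**Conclusion.** The point holds as a defect in how a secondary endpoint would be reported in both cohorts. The rule has an undefined trigger that leaves out deaths, and its natural reading replaces a valid estimate with a table that largely tracks time from response to last assessment. The size is shown by illustration only: with 33 responders and 5 events, one and the same table is compatible with a 6-month DoR of 84.8% (67.4% to 93.4%) or of 100%. Those figures depend on the assumed responder count, response time, accrual and follow-up to cutoff. The underlying argument does not: a censored-only table carries no event times. The primary ORR test and its decision rule are unaffected. The change is worth making, but it is not a threat to the trial's main conclusion.

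**What to change.** Rewrite the last paragraph of SAP 6.2.3, which also governs IC-DoR:

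- Delete few progressions as a reason to leave Kaplan-Meier. The existing listing rule for few responders can stay.
- Report Kaplan-Meier DoR and IC-DoR as in SAP 5.2.17, with numbers of events and of censored responders, and the median as NR if not reached.
- Give landmark rates with log(-log) 95% CIs and numbers at risk: 6 months, and 12 months only where follow-up supports it. If there are no events by the landmark, report 100% and state that no log(-log) CI is estimable.
- Keep the duration bands only as a supplement, over all responders, with events and censored responders in separate columns.

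The cost is one paragraph of SAP text. The methods are already in the SAP, and no extra patients or data are needed.

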6.2.4. Duration of Intracranial Response (IC-DoR) in Both Cohorts

The IC-DoR, will be summarized similar to DoR as described above in the subset of the SA population with at least 1 intracranial lesion. Surgery or radiotherapy of extracranial lesions will not affect the determination of IC-DoR.

6.2.5. Time to Tumor Response (TTR) in Both Cohorts

TTR is defined as the time from first dose to first documentation of objective tumor response (CR or PR). TTR will only be summarized for the subgroup of patients with an objective response. Descriptive statistics mean, median and range will be provided.

6.2.6. Progression-free Survival (PFS) in Both Cohorts

Progression-Free Survival (PFS) is defined as the time from date of first dose to the date of the first documentation PD per RECIST v1.1 as assessed by the independent oncologist and investigator or death due to any cause, whichever occurs first and will be summarized in months:

$$\text{PFS (months)} = [\text{date of event or censoring} - \text{date of first dose} + 1] / 30.4375$$

PFS data will be censored as follows:

- For patients who start a new anti-cancer therapy (as defined in [Section 5.2.6](#)) prior to an event, censoring will be at the last adequate tumor assessment (see [Section 5.2](#)) prior to the start of new anti-cancer therapy. Note: if date of progression occurs on the same date as the start of new anti-cancer therapy, the progression will be counted as an event.
- For patients with documented progression or death after two or more missing tumor assessments, censoring will occur at the last adequate tumor assessment prior to the missing assessments. In this study antitumor activity will be assessed through radiological tumor assessments conducted at screening and every 6 weeks until disease progression regardless of initiation of subsequent anti-cancer therapy. The allowable time window for disease assessments is ± 7 days while on treatment and whenever disease progression is suspected (eg, symptomatic deterioration). Therefore time without adequate assessment is defined as 98 days (12 weeks plus 2 weeks).
- For patients who do not have an adequate baseline tumor assessment or who do not have any post-baseline tumor assessments, censoring will occur on the date of first dose unless death occurred on or before the time of the second planned tumor assessment (ie, on or before Day 98) in which case the death will be considered an event. Note for patients who died without any post baseline assessments and meet the definition of two or more missed assessment the reason for censoring will be documented as two or more missed assessments and censoring will occur on the date of first dose.
- All other patients alive without objective progression will be censored on the date of the last adequate tumor assessment.

The date of tumor response at each nominal timepoint based on the independent radiologist assessments will be used for determining the dates of last adequate for censoring.

The date of tumor response at each nominal timepoint based on the independent radiologist assessments will be used for determining the dates of last adequate assessment for censoring purposes.

The censoring and event date options to be considered for the PFS analysis are presented in [Table 2](#).

Table 2. Outcome and event dates for PFS analyses

Scenario	Date of event/censoring	Outcome
No adequate baseline assessment	Date of first dose	Censored ^a
Progression or death \leq 98 days after last adequate tumor assessment or 98 days after date of first dose	Date of progression or death	Event
Progression or death $>$ 98 days after the last adequate tumor assessment ^b	Date of last adequate assessment b documenting no PD prior to anti-cancer therapy or missed assessments	Censored
No progression		
New anti-cancer therapy given prior to PD		

a. If the patient dies \leq 98 days after date of first dose the death is an event on the death date.

b. If there are no adequate post-baseline assessments prior to PD or death, then the time without adequate assessment should be measured from the date of first dose; if the criteria were met the censoring will be on the start date.

Kaplan-Meier estimates (product-limit estimates) will be presented by Cohort together with a summary of associated statistics including the median PFS time with two-sided 95% CIs. The PFS rate at clinical meaningful timepoints will be estimated with corresponding two-sided 95% CIs. The CIs for the median will be calculated according to Brookmeyer and Crowley² and the CIs for the survival function estimates at the timepoints defined above will be derived using the log(-log) method according to Kalbfleisch and Prentice³ (conftype=loglog default option in SAS Proc LIFETEST). The estimate of the standard error will be computed using Greenwood's formula.

Frequency (number and percentage) of patients with each event type (PD or death) and censoring reasons will be presented by Cohort along with the overall event and censor rates.

Reasons for censoring should be summarized according to the categories in Table 3. If a patient meets multiple definitions for censoring the list will be used to define the hierarchy.

Table 3. Censoring Reasons and Hierarchy

Hierarchy	Condition	Censoring Reason
1	No adequate baseline assessment	No adequate baseline assessment
2	Start of new anti-cancer therapy before event.	Start of new anti-cancer therapy
3	Event more than 98 days from last adequate post-baseline tumor assessment/start date	Event after missing assessments ^a
4	No event and [withdrawal of consent date \geq start date OR End of study (EOS) = Subject refused further follow-up]	Withdrawal of consent
5	No event and lost to follow-up in any disposition page	Lost to follow-up
6	No event and [EOS present OR disposition page for any EPOCH after screening says patient will not continue into any subsequent phase of the study] and no adequate post-baseline tumor assessment	No adequate post-baseline tumor assessment
7	No event and none of the conditions in the prior hierarchy are met	Ongoing without an event

^a more than 98 days after last adequate tumor assessment.

The PFS time or censoring time and the reasons for censoring will also be presented in a patient listing.

Time of Follow-Up for PFS

A Kaplan-Meier summary table for PFS follow-up duration will also be generated to assess the follow-up time in the treatment arms reversing the PFS censoring and event indicators.

CCI [REDACTED]

[REDACTED]

[REDACTED]

[REDACTED]

[REDACTED]

CCI [REDACTED]

[REDACTED]

[REDACTED]

- [REDACTED]
- [REDACTED]
- [REDACTED]
- [REDACTED]
- [REDACTED]
- [REDACTED]

[REDACTED]

CCI [REDACTED]

CCI [REDACTED]

6.2.7. Overall Survival (OS) in Both Cohorts

Overall survival (OS) is defined as the time from date of first dose to the date of death due to any cause. Patients last known to be alive will be censored at date of last contact (see [Section 5.2.7](#)). OS will be summarized in months:

$$\text{OS (months)} = [\text{date of death or censoring} - \text{start date} + 1] / 30.4375$$

OS time associated with Cohort will be summarized using the Kaplan- Meier method (product-limit estimates) and displayed graphically where appropriate. CIs for the 25th, 50th, and 75th percentiles will be reported.

The OS rate at clinical meaningful timepoints will be estimated with corresponding two-sided 95% CIs. The CIs for the median will be calculated according to Brookmeyer and Crowley² and the CIs for the survival function estimates at the timepoints defined above will be derived using the log(-log) method according to Kalbfleisch and Prentice³ (conftype=loglog default option in SAS Proc LIFETEST). The estimate of the standard error will be computed using Greenwood's formula.

Frequency (number and percentage) of patients with an event (death) and censoring reasons will be presented by treatment arm. Censoring reasons are as follows:

- Alive;
- Withdrawal of consent;
- Lost to follow-up.

The OS time or censoring time and the reasons for censoring will also be presented in a patient listing.

Time of Follow-Up for OS

A Kaplan-Meier summary table for OS follow-up duration will also be generated to assess the follow-up time in Cohort reversing the OS censoring and event indicators.

